8.3.3. Additional Therapy

Additional therapy with AU-011 at the maximum tolerated and feasible dose of 3 repeat doses of 80 µg each followed by two laser applications (treatment regimen) can be provided to:

- ensure that all subjects are able to receive the maximum tolerated and feasible dose, particularly for subjects that were treated with lower doses previously
- allow additional treatment regimens in subjects that have stable disease (treatment extension)
- allow retreatment in subjects that meet the protocol definition of disease progression

If the fovea is near the tumor edge, an adjustment to the laser procedure should be performed on each treatment day as outlined in section 8.2.2 and the Injection and Laser Procedure Manual. Subjects may be considered for additional therapy with AU-011 (defined above) after Visit 11 (Week 12) and only after inflammation from the previous treatment has resolved or when the inflammation is minimal and decreasing based on investigator judgement. Additional therapy with AU-011 must be approved by the Sponsor on a case-by-case basis prior to the initiation of therapy. Alternatively, also after Visit 11 (Week 12 Visit), standard of care therapy, including plaque brachytherapy, proton beam radiotherapy or enucleation may be used if the subject meets the protocol definition of disease progression or the Investigator judges that the disease is progressing per their clinical judgement for increases in tumor thickness or LBD that are less than the protocol definition of disease progression. Before additional therapy is performed, the following protocol assessments must be collected in the study eye unless otherwise noted: ETDRS BCVA (both eyes), slit lamp biomicroscopy, IOP measurement, fundoscopy, Fundus photos, EDI-OCT, B-scan ultrasound, A-scan ultrasound, OCTA (Cohorts 6 to 9 only) and a visual field examination. If these assessments have not been performed at the most recent study visit, an unscheduled visit is required to be performed to obtain these assessments.

The criteria for implementing additional therapy due to disease progression is as follows:

• An increase on B-scan ultrasound of >0.5 mm in melanoma thickness from baseline, not due to intralesional hemorrhage/inflammation

OR

• An increase on digital fundus photos of >1.0 mm in melanoma diameter from baseline, not due to intralesional hemorrhage/inflammation or pigmentary changes

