10.3.4. Fluorescein Angiography (FA) and Color Fundus Photography (Fundus Photos)

FA will be performed at Visit 1 (Screening), Visit 11 (Week 12), Visit 14 (Week 52), and Visit 16 (Week 104), and at any Early Termination Visit. Fundus photos will be performed in **both eyes** at Visit 1 (Screening) and Visit 11 (Week 12), and at any Early Termination Visit if that occurs before Visit 11 (Week 12). Fundus photos will be taken for the study eye only at all other visits including Early Termination that occurs after Visit 11 (Week 12). All FAs and fundus photos will be performed using digital fluorescein photography equipment and cameras certified by the IRC. The IRC will certify all photographers performing FA and fundus photos before they perform any imaging on study subjects. The IRC will provide each site with the protocol for image acquisition and transfer.

The largest basal diameter (LBD) of the CM will be measured on the Fundus Photos at baseline and all visits described above. The greatest basal area (GBA) of tumor will also be measured on Fundus Photos at the same visits and tumor volume will be derived using the GBA and the maximum tumor thickness (measured by B-scan ultrasound) using the formula $\pi r^2 h/3$ where r is the radius derived from the GBA and h is the maximum tumor thickness. The criteria to classify tumor response (diameter) on Fundus Photos will be:

Tumor Control:

- Regression = Any reduction > 0.5 mm in the largest basal diameter (LBD) of the CM from baseline
- Stable Disease (SD) = Maximum LBD of the CM is within \geq -0.5 mm to \leq +1.0 mm change in diameter from baseline

Tumor Progression:

• Progression = Any increase > 1.0 mm in the LBD of the CM from baseline not judged by the Investigator to be due to inflammation/swelling, hemorrhage or pigmentary changes

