10.3.7. B-scan Ultrasound

B-scan ultrasound (B-scan) will be performed in **both eyes** at Visit 1 (Screening) and Visit 11 (Week 12), and at any Early Termination Visit if that occurs before Visit 11 (Week 12) and in the study eye only at Visit 2 (Day 1), Visit 3 (Day 2) for cohorts 1, 2 and 3 only, Visit 4 (Day 8), Visit 6 (Day 15), Visit 8 (Day 29), Visit 10 (Week 8), Visit 12 (Week 26), Visit 13 (Week 39), Visit 14 (Week 52), Visit 15 (Week 78), Visit 16 (Week 104), and at any Early Termination that occurs after Visit 11 (Week 12). Ultrasound technicians will be certified by the IRC prior to study initiation based on adherence to IRC provided imaging acquisition and transfer protocols. Tumor thickness eligibility for the study is determined by B-scan measurement.

Criteria to classify tumor response (thickness) on B-scan will be:

Tumor Control:

- Complete Response (CR) = Entire tumor is a flat lesion and of equal (or less) thickness to the surrounding choroid
- Regression = Any reduction > 0.5 mm in the maximum thickness of the CM from baseline
- Stable Disease (SD) = Maximum thickness of the CM is within \geq -0.5 mm to \leq +0.5 mm change from baseline

Tumor Progression:

• Progression = Any increase > 0.5 mm in the maximum thickness of the CM from baseline not judged by the Investigator to be due to inflammation/swelling or hemorrhage

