#### 2. Based on maximum thickness and LBD, subject receiving Standard of Care, and Investigators determination of progression

Confidential

Tumor response (PR, SD, or DP) will be based on the algorithm defined method 1 above with the addition of the Investigator determination of progression criteria provided in Section 8.1.2.

3. Based on maximum thickness and LBD, subject receiving Standard of Care, Investigators determination of progression, and adverse events of pigmentary changes

Tumor response (PR, SD, or DP) will be based on the algorithm defined method 1 with the additional criteria of both Investigator determination (Section 8.1.2) and AE of pigmentary changes provided in (Section 8.1.3).

As this method accounts for the Investigator determination of progression per protocol sections 10.3.4 and 10.3.7, it will be considered the primary method for describing the results in the clinical study report.

For each of these 3 methods of determining tumor response, the tumor response results will be presented at each visit, as well as an overall summary table. The overall summary table will present the results at Month 12 using last observation carried forward (LOCF) as well as the subject's last visit, including follow-up. For the overall summary table, the table will provide which of the LBD and maximum thickness criteria were met for the response (or both) as well as a category for "Treated with standard of care prior to Progression" (i.e., this category will be for subjects who were treated with standard of care prior to reaching the progression criteria).

An additional summary of the Summary of Tumor Response Tables (3 tables for Methods 1-3) including just site 009 (i.e., the site excluded from the Efficacy Evaluable Population) will be performed.

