#### **8.1.2 Investigator Determination of Progression**

The investigator determination of progression is based on the corresponding Investigator judgement of progression eCRF question:

*Did the subject meet the protocol defined disease progression criteria and not yet receive additional therapy with standard of care (plaque brachytherapy, proton beam radiotherapy or enucleation) or additional therapy with AU-011 since the previous visit? (Yes/No Response).*

If the Response to this eCRF question is "No" and the subject met the criteria for disease progression (DP) based on the maximum thickness and LBD criteria defined in Section 8.1.1, then the tumor response will be classified as Stable Disease (SD).

Note that if a subject has started standard of care, they will be considered as having met the disease progression (DP) criteria from the date standard of care was administered.

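### SAP 8.1.2 turns measured progression into stable disease on any 'No' to a compound eCRF item that records no cause, so cancellations the protocol excuses cannot be told from others, and the error can only raise tumor control

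*SAP*

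**What the plan says.** **Protocol.** A thickness increase above 0.5 mm is progression when it is "not judged by the Investigator to be due to inflammation/swelling or hemorrhage" (10.3.7). An LBD increase above 1.0 mm is progression when it is "not judged by the Investigator to be due to inflammation/swelling, hemorrhage or pigmentary changes" (10.3.4). Pigment therefore excuses LBD but not thickness. The progression criteria for additional therapy in 8.3.3 have the same split; only the diameter limb ends with "not due to intralesional hemorrhage/inflammation or pigmentary changes".

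**SAP.** Section 8.1.1 repeats these cause clauses. Method 1, on which Methods 2 and 3 are built, sets the Investigator part aside. Section 8.1.2 then brings the Investigator back through an eCRF item that begins "Did the subject meet the protocol defined disease progression criteria and not yet receive additional therapy with standard of care" and goes on to ask the same about additional AU-011 since the previous visit. The answer is Yes or No. A 'No' alongside measured DP gives stable disease: "criteria defined in Section 8.1.1, then the tumor response will be classified as Stable Disease (SD". Recipients of standard of care stay DP from the date it was given. A missing answer is filled from the next available one.

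The measurements being overridden are averages over two or three readers without adjudication (SAP 8). Method 3 includes the 8.1.2 rule and is made primary with this reason: "As this method accounts for the Investigator determination of progression per protocol sections 10.3.4 and 10.3.7, it will be considered the primary method".

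**The concern.** The protocol gives the Investigator one task: to decide whether a measured increase has one of a short list of causes, a list that differs between thickness and LBD. The SAP replaces that with an answer to a broader question and keeps no record of why the answer was 'No'. If a 'No' has some other origin, a progression that the protocol would count becomes tumor control.

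This matters because the rule has no counterpart in the other direction. Nothing in 8.1.2 moves stable disease to DP on a 'Yes', so disagreements cannot offset each other. The result enters the tumor control proportion that the clinical study report will present as primary.

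**Working it through.** The plan gives no figure to reproduce: the study is descriptive, and SAP 3.3 states that no formal sample size calculation was made. The check sets the two rules side by side.

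**1. Protocol rule against SAP 8.1.2.** Take an increase over the threshold, no standard of care, and the answer 'No'. The protocol column uses 10.3.4 and 10.3.7, with non-progression counted as stable disease (SD), as protocol 10.5 does.

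| Dimension | True cause | Protocol | SAP 8.1.2 on 'No' | Same? |
|---|---|---|---|---|
| Thickness | inflammation/swelling | SD | SD | yes |
| Thickness | hemorrhage | SD | SD | yes |
| Thickness | pigment | DP | SD | no |
| Thickness | none of these | DP | SD | no |
| LBD | inflammation/swelling | SD | SD | yes |
| LBD | hemorrhage | SD | SD | yes |
| LBD | pigment | SD | SD | yes |
| LBD | none of these | DP | SD | no |

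The rules differ in 3 of the 8 combinations, and nothing in 8.1.2 separates those 3 from the other 5. This counts rule combinations, not subjects. An Investigator who applies the protocol criteria exactly, to the same measurements as the readers, would not answer 'No' in those three rows.

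**2. What a literal 'No' can mean.** Let M = met the protocol criteria, S = standard of care given, A = additional AU-011 given since the previous visit. The item asks whether M holds and neither S nor A has happened, so 'No' means: not M, or S, or A.
- S is handled: 8.1.2 keeps the subject as DP.
- A is not handled. With M and A both true, the literal answer is 'No' and measured DP becomes SD. Protocol 8.3.3 allows AU-011 retreatment after progression, so the case can occur. Protocol Appendix 4 names the planned second cycle separately from additional therapy, so this route concerns 8.3.3 retreatment.
- Not M covers both an excused cause and a disagreement about the size of the increase.

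**3. The pigment limit in 8.1.3.** That section confines its conversion to DP met on LBD alone, with a pigmentary adverse event and a 'No' on or after its start. Method 3 also applies 8.1.2, which already cancels DP in either dimension on a same-visit 'No' without any adverse event. The limit therefore has little effect.

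**4. Direction.** Both 8.1.2 and 8.1.3 move subjects only from DP to SD. At any timepoint, therefore, tumor control under Method 1 ≤ Method 2 ≤ Method 3, and Method 2 minus Method 1 is the number of DPs cancelled by 8.1.2.

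**5. Size per cancelled DP (100 × k / n).**

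| Cancelled DPs (k) | n = 60 (planned total, approximate) | n = 15 (Cohort 12 maximum) |
|---|---|---|
| 1 | 1.7 points | 6.7 points |
| 2 | 3.3 points | 13.3 points |
| 3 | 5.0 points | 20.0 points |

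The documents do not say how many there are.

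**The case against.** The best defence is that the eCRF item asks about protocol-defined criteria, and those criteria contain the excused causes, including the restriction of pigment to LBD. An Investigator who follows them answers 'No' to a measured increase because of an excused cause. The protocol also leaves the cause to the Investigator's judgement and requires no adverse event or examination finding. On this view only the documentation of cause is missing. In addition, Method 1 is tabulated beside Methods 2 and 3, the overall tables show which dimension was met, individual values are listed, SAP 4.9 says the response criteria differ from the protocol's, and no hypothesis is tested.

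Much of this stands, and it rules out several stronger readings that a reader might infer:
- *That the SAP permits pigment to excuse thickness.* It does not say so. The rule only fails to prevent it if the item is answered that way.
- *That Investigators answer from site measurements which differ from the readers'.* No section says which measurements they use. The 0.4 mm and 0.3 mm margins in inclusion criterion 5C do not supply a disagreement rate, because they concern the clinical site and the referring center, not the site and the central readers.
- *That the rationale for Method 3 is false.* It says the method accounts for the Investigator's determination, not that it reproduces the protocol rule.

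The defence does not dispose of the rest. Inclusion by reference shows that some 'No' answers are excused, not that all are. The retreatment route follows from the item's own wording. The Method 1 comparison gives the total cancelled but mixes excused and other cancellations. The disclosure in 4.9 is general and does not name this change.

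**Conclusion.** The concern holds as a defect of traceability with a one-way effect. SAP 8.1.2 can cancel progression that the protocol would count, and the collected answer does not show when it has. The effect on tumor control is zero or upward, at the per-subject sizes shown above. The Cohort 12 size assumes that the cohort fills to 15.

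A reader might go on to conclude that the primary control rate is inflated by a material amount. The documents do not support that: the number of cancelled DPs is not given and may be zero, and the share with an excused cause is unknown. The mismatch between the rules rests on no assumption about measurement error.

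Nor do the documents support replacing the Investigator's judgement in the primary method with a requirement for adverse event or examination evidence. The protocol contains no such requirement, and the recorded data would miss some excused increases. The B-scan fields described in SAP 8.4.3 have no intralesional hemorrhage item, fundoscopy is summarized only as normal or abnormal (SAP 9.6.5), and in Cohorts 1 to 9 adverse events after 30 days are reported only if related (protocol 10.2.3.3).

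**What to change.** 1. In the Method 2 and Method 3 tables, add the number of DPs cancelled under 8.1.2. Split it by dimension (thickness, LBD, both) and by excused cause documented at that visit (inflammation/swelling, hemorrhage, or a pigmentary adverse event for LBD only) or none.
2. Add a labelled sensitivity version of Method 3. In it, 'No' converts DP to SD only where a cause that the protocol excuses for that dimension is documented, and a 'No' that may reflect only earlier AU-011 retreatment leaves DP in place.
3. Reword the reason given for making Method 3 primary, so that it does not imply that the method applies the cause-limited rule of protocol 10.3.4 and 10.3.7.

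The primary derivation stays as it is. The cost is SAP wording, some table rows and one further derivation from adverse event, slit lamp (anterior chamber cells, vitreous haze), fundoscopy, B-scan and retreatment records already collected. There are two drawbacks to state in the report. Some truly excused increases will have no documented cause, so the sensitivity control rate should be read as a lower bound beside Method 3. And SAP v5.0 already follows the first database lock of 25 August 2021, so the analysis is a post-lock addition and must be labelled as one.

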### **Missing Investigator judgement of progression:**

If the subject is missing the Investigator judgement of progression for a visit, the values from the subject's next non-missing Investigator judgement of progression will be used. If the subject does not have a next non-missing assessment (i.e., there are no subsequent assessments or they are all missing), the determination of the tumor response category will be based on the LBD and maximum thickness criteria values only (i.e., without consideration of the Investigator judgement of progression).

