#### 1. Based on maximum thickness and LBD and subject receiving Standard of Care

Tumor response (PR, SD, or DP) will be based on the algorithm as defined in Section 8.1.1, with the modification that Investigator determination mentioned in DP definition will not be considered and if a subject receives standard of care they will be considered as having met the disease progression (DP) criteria from the date standard of care was administered.

Note that for the Month 12 LOCF and Last Visit timepoints:

- If a patient receives standard of care prior to their Month 12 Visit, the subject will be considered as having met DP, even if the LBD and/or tumor thickness assessments are being LOCF'd from a time-point previous to the SOC being administered.
- Similarly, if a patient receives standard of care prior to their Last Visit, the subject will be considered as having met DP, even if the LBD and/or tumor thickness assessments are being LOCF'd from a time-point previous to the SOC being administered.

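### Back-filling a missing Investigator judgement from a later visit can relabel measured progression as stable disease in Method 2 and, to an extent that depends on its wording, in primary Method 3

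*SAP*

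**What the plan says.** SAP 8.1 defines three ways of classifying tumour response.

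- Method 1 uses thickness, LBD and receipt of standard of care; the "Investigator determination mentioned in DP definition will not be considered".
- Method 2 is Method 1 "with the addition of the Investigator determination of progression criteria provided in Section 8.1.2".
- Method 3 is Method 1 "with the additional criteria of both Investigator determination (Section 8.1.2) and AE of pigmentary changes provided in (Section 8.1.3"). Of Method 3 the SAP says "it will be considered the primary method for describing the results in the clinical study report".

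Section 8.1.2 takes the judgement from a yes/no eCRF question. If the answer is 'No' and the measurements meet DP, "then the tumor response will be classified as Stable Disease (SD"). The question is compound. It asks whether the progression criteria were met and also whether the subject has not yet received standard of care "or additional therapy with AU-011 since the previous visit".

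If the answer is missing at a visit, "the values from the subject's next non-missing Investigator judgement of progression will be used". Only when no later answer exists does the SAP fall back on the data from the visit itself: "the determination of the tumor response category will be based on the LBD and maximum thickness criteria values only" (that is, without the judgement).

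Section 8.1.2 also sets DP from the date standard of care was given. Under Method 1, on which the other two are built, standard of care before Month 12 or before Last Visit forces DP at that timepoint.

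**The concern.** Under SAP 8.1.1 and Protocol 10.3.4 and 10.3.7, a measured increase is excused only if the Investigator judged it to be due to inflammation or swelling, hemorrhage or, for LBD, pigmentary change. An answer borrowed from a later visit is not a judgement of the earlier increase. By then the tumour may have a different size.

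The compound question adds a second difficulty. A 'No' may mean that the criteria were not met, or that therapy has been given since the previous visit. Protocol 8.3.3 allows AU-011 retreatment because of progression. A subject could progress at a visit with no recorded judgement, be retreated, and be answered 'No' at the next visit. That 'No' would then be carried back over the very progression that led to retreatment. Standard of care has a DP rule of its own from its start date; AU-011 retreatment has none.

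Classification also comes to depend on length of follow-up. SAP 4.2 places the final analysis after all subjects complete Week 52, because the study ended early. Two subjects with the same Week 52 measurements and no Week 52 judgement would differ: one with no later answer stays DP, and one with a later 'No' becomes SD.

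**Working it through.** The plan gives no figure to reproduce here: SAP 3.3 states that no formal sample size calculation was made. The check applies the rules of SAP 8.1, 8.1.1, 8.1.2 and 8.1.3 to hypothetical subjects.

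**Which measured DP is changed.** Take a Week 52 measurement that meets DP, no Week 52 judgement, 'No' at Week 78 and no standard of care. The DP limits are an increase above 0.5 mm in thickness or above 1.0 mm in LBD. Method 3 is shown on two readings: 8.1.2 and 8.1.3 applied separately, or both required together.

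| Week 52 finding | Method 1 | Method 2 | Method 3, separate | Method 3, together |
|---|---|---|---|---|
| Thickness +0.7 mm | DP | SD | SD | DP |
| LBD +1.3 mm, no pigmentary event | DP | SD | SD | DP |
| LBD +1.3 mm, pigmentary event already begun | DP | SD | SD | SD |

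If the Week 78 answer is 'Yes', or no later answer exists, every cell is DP. If standard of care has already been given by Week 52, every cell is DP. If a missing judgement simply leaves the measured category in place, every cell is also DP. So, relative to measurement-only classification, the fill moves results in one direction.

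**How far the answer is carried.** The target days in SAP 11.2 are 85, 183, 274, 365, 547 and 728 for Weeks 12, 26, 39, 52, 78 and 104.

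- Week 12 to 26: 183 − 85 = 98 days (14 weeks)
- Week 26 to 39: 274 − 183 = 91 days (13 weeks)
- Week 39 to 52: 365 − 274 = 91 days (13 weeks)
- Week 52 to 78: 547 − 365 = 182 days (26 weeks)
- Week 78 to 104: 728 − 547 = 181 days (about 26 weeks)
- Week 52 to 104, if Week 78 is also missing: 728 − 365 = 363 days

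**Standard of care between the two visits.** Suppose DP is measured at Week 26 with no judgement, standard of care follows, and Week 39 is answered 'No'. The Week 26 by-visit row becomes SD in Method 2. From the date of standard of care the subject is DP, and is DP at Month 12. What can change is the earlier row and possibly the label in the overall table, where the subject could be counted as treated with standard of care before progressing.

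**Size per subject.** One subject is 1/15 = 6.7 percentage points in Cohort 12 at its maximum of 15, and 1/60 = 1.7 points in about 60 subjects.

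**The case against.** The one-way action belongs to 8.1.2 itself: an observed 'No' also only removes DP, and an observed 'Yes' also changes nothing. That is correct, but an observed 'No' is a judgement of that visit's increase and a borrowed one is not.

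A reader might infer that missing data can only improve the primary result. The documents do not support that. If the increase was swelling and the missing answer would have been 'No', then a later 'Yes', or no later answer, leaves DP, and missingness has made the response worse. The one-way statement holds only against the measured category.

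The back-fill has some rationale. The question looks back over the interval since the previous visit, and a later 'No' with no therapy in between is some evidence that the earlier increase was transient. But the rule requires neither an absence of intervening therapy nor any link to the earlier measurement.

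Method 1 is tabulated by visit and overall, and the difference between Methods 1 and 2 caps the back-fill effect. It does not isolate it, because Method 1 drops every judgement, including those made at the visit. None of the sensitivity analyses in SAP 8.3 addresses missing judgements.

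It also stands that safety is the primary objective, that efficacy is descriptive, that the 26-week gaps arise only after Week 52, and that a change to the derivation now comes after a database lock.

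**Conclusion.** The point holds with limits. A missing judgement followed by a 'No' relabels measured DP as SD without any judgement of that visit's increase. Method 2 is affected for any measured DP. Method 3 is affected to the same extent if 8.1.2 and 8.1.3 apply separately. If both must be met together, only DP on LBD alone with a pigmentary adverse event is affected, and thickness DP stays DP.

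Two further inferences go beyond the text. One is that subjects given standard of care escape DP in the overall summary: standard of care before Month 12 or Last Visit forces DP there. The other is that an answer given after standard of care must be 'No': the compound question can be parsed in more than one way, so 'No' is possible but not certain.

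The total effect cannot be determined, because the documents do not say how many judgements are missing; the number could be zero. The per-subject figure of 6.7 points assumes that Cohort 12 reaches 15 subjects.

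**What to change.** Replace the back-fill in SAP 8.1.2: when the judgement is missing at a visit, classify that visit on thickness, LBD and standard of care only, as the SAP already does when no later answer exists. State whether 8.1.2 and 8.1.3 apply separately or together in Method 3. State also that 8.1.3 uses the answer from the same visit, since its text asks only for a 'No' on or after the start of the event. Report the number of DP visits with a missing judgement.

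SAP v5.0 was written after the first database lock, so document this as a post-lock change. Show the back-filled version alongside, with the count of DP-to-SD changes that it makes.

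The cost is a short text change, a simpler derivation and one extra set of results. Tumour control may look slightly less favourable, and some true swelling at visits with no recorded judgement would stay DP.
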